## 10.2. Safety analysis

Name of data	Derivation and calculation method
Adverse events	Of events described in “Humira BD_AE matching list (for application for reassessment)(after linking)_20170110”, events derived from survey sheet or events listed in detailed survey report described by physician of contracted departments and institutions although they are not derived from survey sheet are deemed to be adverse events included in analysis. Adverse events occurred: At least one record of adverse event is found. No adverse event: Other than above When the number of adverse events is counted, in a case where the events are aggregated by SOC, the events expressed in same SOC in the same patient is deemed as 1 event, and in a case where they are aggregated by PT, the events expressed in same PT in the same patient is deemed as 1 event. If there is no applicable patient, “0” for the number of patients and “0.00” for rate of patients should be displayed.

Name of data	Derivation and calculation method
Serious adverse events	
Of adverse events, those assessed as serious using seriousness criteria for company's seriousness assessment described in "Humira BD_AE matching list (reassessment) (after linking)_20170110" are deemed as serious adverse events.
 
Serious adverse events occurred: At least one record of serious adverse event is found.
 
No adverse event: Other than above
 
The same counting method as that for adverse events shall be used for the number of serious adverse events.

Adverse reaction	
Of adverse events, adverse events except for those assessed as "Not related" based on criteria for company's causality assessment described in "Humira BD_AE matching list (reassessment) (after linking)_20170110" are deemed to be adverse reaction.
 
Adverse reactions occurred: At least one record of adverse reaction is found.
 
Adverse reactions did not occur: Other than above
 
The same counting method as that for adverse events shall be used for the number of adverse reactions.

Serious adverse reactions	
Of adverse events, those assessed as serious using seriousness criteria for company's seriousness assessment described in "Humira BD_AE matching list (reassessment) (after linking)_20170110" are deemed as serious adverse reactions.
 
Serious adverse reactions occurred: At least one record of serious adverse reaction is found.
 
Serious adverse reactions did not occur: Other than above
 
The same counting method as that for adverse events shall be used for the number of serious adverse reaction.

Outcome	
When adverse event, adverse reaction, serious adverse event, and serious adverse reaction are aggregated by outcome, if multiple events with same SOC or those with same PT were present in 1 patient, such events should be identified using outcome in company's outcome assessment described in "Humira BD_AE matching list (reassessment) (after linking)_20170110" according to the priority as follows:
 
[1] Death [2] Sequela [3] Not resolved [4] Unknown [5] Not described [6] Resolving [7] Resolved

Days from the start date of the initial administration of this drug until the onset date of adverse event	
Onset date described in company's assessment in "HumiraBD_AE matching list (for reassessment) (after linking)_20170110" should be used. Derivation can be executed if the start date of the initial administration of this drug and onset date of adverse event is identified with complete date.
 
If the start date of the initial administration of this drug is the same as or earlier than the onset date of the adverse events:
 
The onset date of adverse event - the start date of the initial administration of this drug + 1

Name of data	Derivation and calculation method
	
The start date of the initial administration of this drug is later than the onset date of adverse event:
 
The onset date of adverse event - the start date of the initial administration of this drug
 
If there are multiple events with same PT in 1 patient, the onset date of the event that occurred first should be used to identify the events to be aggregated.

Days from the onset date until the outcome (resolved or resolving) date of the adverse event	
Outcome (resolved or resolving) date described in “HumiraBD_AE matching list (for reassessment) (after linking)_20170110” should be used.
 
Derivation can be executed if the onset date and outcome date of adverse event are identified with complete date.
 
Outcome date - onset date of the adverse event + 1
 
If there are multiple events with same PT in 1 patient, the value of the event with the longest duration until the outcome of resolved or resolving should be used.

Incidence of adverse reactions, serious adverse reactions, adverse events, and serious adverse events	
Incidence of adverse reactions, serious adverse reactions, adverse events, and serious adverse events should be calculated by using the number of patients in whom at least one of these events occurred as a numerator and the number of patients included in safety analysis as denominator.
 
If different calculation method from above method is used, it should be described in each table in the Chapter 13 and subsequent chapter.

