## 2. ■ 2. Definition of terms and abbreviations

Terms and abbreviations used in this analysis plan are defined as follows:

Terms and abbreviations	Definition
Patients who were followed up for 52 weeks (patients collected for the first volume)	Patients who started to receive this drug between August 16, 2014 and August 15, 2015.
Patients included at the 104th week of follow-up (patients collected for the first and second volume)	Patients who started to receive this drug between August 16, 2013 and August 15, 2014.
Patients included at the 156th week of follow-up (patients collected for the first, second, and third volume)	Patients who started to receive this drug by August 15, 2013.
Adverse events	Any unfavorable and unintended sign (including an abnormal laboratory finding), symptom, or disease, regardless of whether they are related to this drug or not
Adverse events that occurred during the period subject to safety analysis	
Adverse events that occurred from the start date of administration until the time as follows should be included.
 
 
Patients included at the 52th week of follow-up: The start date of administration of this drug + 392 days (56 weeks)
 
Patients included at the 104th week of follow-up: The start date of administration of this drug + 756 days (108 weeks)
 
Patients included at the 156th week of follow-up: The start date of administration of this drug + 1120 days (160 weeks)
 
Patients who discontinued to receive this drug: The last date of administration of this drug + 28 days
 

Adverse events that occurred in a period except for the period subject to safety analysis	
Adverse events that occurred before the start date of administration or after the following timing should be included
 
 
Patients included at the 52th week of follow-up: The start date of administration of this drug + 392 days (56 weeks)
 
Patients included at the 104th week of follow-up: The start date of administration of this drug + 756 days (108 weeks)
 
Patients included at the 156th week of follow-up: The start date of administration of this drug + 1120 days (160 weeks)
 
Patients who discontinued to receive this drug: The last date of administration of this drug + 28 days
 

Adverse reaction	Among adverse events, those for which causal relationship with this drug cannot be ruled out should be included

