#### “2.4.2 List of occurrence status of events defined as primary survey item (adverse reaction)”

Patients included in analysis: Patients included in safety analysis

Objective of analysis: In adverse reactions that occurred in the period subject to safety analysis, summary statistics of days to onset of the reactions, the number of patients by the outcome, and days to outcome (Resolved or resolving) is shown.

Analysis items: The number of patients in whom adverse reactions occurred and rate of these patients to those included in safety analysis, the number of patients in whom serious adverse reactions occurred and rate of these patients to those included in

analysis by types of the adverse reactions in the period subject to safety analysis should be calculated. In addition, summary of statistics (the number of patients, the mean, median, maximum values) of days to onset of adverse events by PT and primary survey items (the number of PT code), the number of patients by outcome, summary of statistics of days from onset to outcome (Resolved or resolving) (the number of patients, the mean, median, minimum, and maximum values) should be calculated.

Notes: If there are events with same PT in one patient, “2.4.1 List of occurrence status of primary items” should be referred to.

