**“2.9 Incidence of adverse reactions (serious adverse reaction and adverse reaction) by patient characteristics”**

Patients included in analysis: Patients included in safety analysis

Objective of analysis: Incidence of adverse reactions should be shown by patient characteristics and factor analysis should be conducted.

Analysis items: In patients in whom adverse reactions occurred in the period subject to safety analysis, the number of all the patients, the number of patients with serious adverse reactions, and rate of these patients to those included in analysis, the number of the patients with adverse reactions and rate of these patients to those included in analysis, and test provided for the adverse reactions (Fisher’s exact test for nominal scale factors, and Mann-Whitney u test for ordinal scale factors) should be calculated by following patient characteristics:

Notes: Patient characteristics are as follows: Age (years), sex, disease duration (years), complication, hepatic function disorder as complication, renal impairment as complication, medical history, allergy history, smoking habit, self-administration as administration status of this drug, previously used drug/previous treatment, biological preparation adalimumab as previously used drug, biological preparation infliximab as previously used drug, steroid as previously used drug, immunomodulative drug as previously used drug, immunosuppressive drug as previously used drug, oral adrenocortical steroid as concomitant drug, oral mucosa recurrent aphthous ulcer as main symptoms of Behcet disease other than gastrointestinal symptoms, cutaneous symptoms as main symptoms of Behcet disease other than gastrointestinal symptoms, eye symptoms as main symptoms of Behcet disease other than gastrointestinal symptoms, ulcer of vulva as main symptoms of Behcet disease other than gastrointestinal symptoms, arthritis without deformity or rigidity as accessory symptoms of Behcet disease other than gastrointestinal symptoms, epididymitis as accessory symptoms of Behcet disease other than gastrointestinal symptoms, vascular lesion as accessory symptoms of Behcet disease other than gastrointestinal symptoms, moderate or higher degree central nervous lesion as accessory symptoms of Behcet disease other than gastrointestinal symptoms, diagnostic classification of Behcet disease, days until the last date of the administration, and mean daily dose.

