**“2.17 List of occurrence status of adverse reactions and infections in this survey”**

Patients included in analysis: Patients included in safety analysis

Objective of analysis: Occurrence status of adverse reactions and serious adverse reactions is shown.

Analysis items: In adverse reactions that occurred in the period included in safety analysis, adverse reactions and serious adverse reactions should be aggregated for following items.

The number of patients included in the survey, the number of patients in whom adverse reactions occurred, the number of adverse reactions, rate of patients in whom adverse reactions occurred, the number of patients in whom adverse reactions occurred and rate of these patients in those included in the survey by types of the reactions (SOC, PT) should be calculated.

Notes: If there are events with same PT in one patient, these events should be counted as 1 event (1 patient) according to following rules for seriousness.

Priority for seriousness: Serious > non-serious

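### SAP 10.2 derives serious adverse reactions without a causality condition, so they are the same records as serious adverse events

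*SAP*

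**What the plan says.** Four derivation rows in SAP 10.2 matter here.

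- **Serious adverse events.** From all adverse events, those the company's assessment calls serious "are deemed as serious adverse events".
- **Adverse reaction.** This row begins "Of adverse events, adverse events except for those assessed as" and then names the category *Not related* in the company's causality assessment. It therefore removes unrelated events.
- **Serious adverse reactions.** From all adverse events, those the company's assessment calls serious "are deemed as serious adverse reactions".
- **Incidence.** For each of the four event classes the rule takes "the number of patients in whom at least one of these events occurred as a numerator", over the number of patients in the safety analysis.

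Section 2 defines an adverse reaction as follows: "Among adverse events, those for which causal relationship with this drug cannot be ruled out should be included". It has no separate entry for a serious adverse reaction, so the 10.2 row is the only derivation available for that term.

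In Section 13.2 the tables are framed in two ways. Table 2.9, by patient characteristics, is introduced with "In patients in whom adverse reactions occurred in the period subject to safety analysis". Table 2.4.2 is introduced with "In adverse reactions that occurred in the period subject to safety analysis", and Table 2.4.3 follows the same pattern. Table 2.17 also starts from reactions in the safety period and says "adverse reactions and serious adverse reactions should be aggregated for following items".

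**The concern.** A serious adverse reaction should be an adverse reaction that is also serious. The 10.2 row tests seriousness only. It repeats the serious adverse event rule under another label and so brings back the events that the adverse reaction row has just removed.

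The SAP treats adverse events, serious adverse events, adverse reactions and serious adverse reactions as four classes, each with its own incidence. Under the literal rule two of the four are always the same set. A patient can also be recorded as having a serious adverse reaction and no adverse reaction.

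Adverse reactions under actual use are a stated objective of the survey (Section 4.1), and the results go to the regulator for reassessment (Section 3.1). The error runs one way: it attributes to the drug serious events that the company judged unrelated. Tables drawn from different frames could also report different serious counts in the same submission.

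**Working it through.** The SAP gives no figure to reproduce, so the check compares the rules and then follows their logic.

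**Rules side by side (SAP 10.2)**

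| Row | Starting set | Seriousness condition | Causality condition |
|---|---|---|---|
| Serious adverse events | all adverse events | company: serious | none |
| Adverse reaction | all adverse events | none | company: other than *Not related* |
| Serious adverse reactions | all adverse events | company: serious | none |

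The first and third rows match in every column, so they return the same records for any data. The two incidences have the same numerator and the same denominator, and are therefore always equal.

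**Which patients are misflagged**

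A patient may or may not have each of four kinds of event: related serious (RS), related non-serious (RN), unrelated serious (US) and unrelated non-serious (UN). That gives 2^4 = 16 profiles.

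- Flag as written: RS or US. It is set in 16 − 4 = 12 profiles, exactly those with a serious adverse event.
- Flag consistent with the adverse reaction row: RS. It is set in 8 profiles.
- Difference: 12 − 8 = 4 profiles, all with US present and RS absent (RN and UN are free: 2 × 2 = 4).
- In 2 of these 4, RN is also absent, so the patient has a serious adverse reaction but no adverse reaction.

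**Effect by table frame**

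- Table 2.9 read literally, as patients with any reaction (RS or RN): 12 profiles remain. Misflagged are those with RS absent, RN present and US present, with UN free: 2 profiles.
- Tables framed on the reactions themselves (2.4.2, 2.4.3, 2.17 and the by-seriousness tables): US records are dropped before seriousness is read, so 0 profiles are misflagged.

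These are counts of logical cases, not error rates.

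**Illustration with assumed values**

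Let s be the proportion of patients with a serious adverse event, and u the share of those patients with no related serious event. The rate as written is s; the corrected rate is s × (1 − u). The SAP gives neither value. Taking s from 10% to 30% and u from 20% to 60%:

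- lowest corrected rate: 10% × (1 − 0.6) = 4%, against 10% as written;
- highest corrected rate: 30% × (1 − 0.2) = 24%, against 30% as written.

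This shows how the error scales. It is not an estimate for this survey.

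**The case against.** The intended meaning is hardly in doubt. Section 2 and the adverse reaction row both define a reaction by causality. The Table 2.9 title, Table 2.17 and the by-seriousness tables all treat serious reactions as a subset of reactions. This looks like a copying slip that a careful programmer would notice.

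The reach is also limited. The 10.2 incidence is a calculation rule, and results appear only in the Section 13 tables. Of the four tables that count serious adverse reactions by name (2.4.2, 2.4.3, 2.9, 2.17), three start from reactions. The remaining exposure is mainly one descriptive column of Table 2.9.

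Even there the wording is loose. The introductory phrase also governs the total number of patients, and a test of reactions across characteristics needs patients without reactions, so it cannot be a strict filter for the whole table.

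The points on intent and reach stand, and they keep this from being a major defect. They do not remove it. The general definitions contradict the operative row rather than correct it, and nothing else in the SAP repairs it. The loose wording of Table 2.9 cuts both ways: if the phrase means reactions, no profile is misflagged; if it filters nothing, all 4 are.

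**Conclusion.** The row is wrong as written and should be fixed. That its selection duplicates the serious adverse event rule, and that the two incidences are therefore equal, follows from the text and needs no assumption about the data.

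The exposure of Table 2.9 rests on reading its introduction literally, as a restriction on patients. The safety of Tables 2.4.2, 2.4.3, 2.17 and the by-seriousness tables rests on their being programmed from adverse reactions, not from the 10.2 flag. The Table 2.9 tests compare adverse reactions, so no p value is affected.

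Any error raises the serious adverse reaction count and never lowers it. Its size depends on how many patients had an unrelated serious event and no related one, which the SAP does not show.

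**What to change.** 1. In the 10.2 row for serious adverse reactions, make the starting set adverse reactions as derived in the preceding row. Leave the seriousness criterion and source list unchanged. The incidence rule then needs no edit.
2. In Table 2.9, state that the serious column counts patients with at least one adverse reaction that is itself serious.
3. Before producing Tables 2.4.2, 2.4.3, 2.9 and 2.17, check in the program that serious adverse reactions are a subset of both adverse reactions and serious adverse events.

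The cost is one word in 10.2, one clause in Table 2.9 and one program check. No new data are needed.

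### Table 2.9 compares crude adverse-reaction proportions across patient factors without allowing for safety windows of 56, 108 or 160 weeks set by start date, so factors associated with start date are confounded with observation time.

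*SAP*

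**What the plan says.** Section 2 assigns each patient to a follow-up class by the date treatment began. For example, the 52-week class is "Patients who started to receive this drug between August 16, 2014 and August 15, 2015". The class fixes how long adverse events are counted:

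- 52-week class: "The start date of administration of this drug + 392 days (56 weeks").
- 104-week class: "The start date of administration of this drug + 756 days (108 weeks").
- 156-week class: "The start date of administration of this drug + 1120 days (160 weeks").
- Patients who stopped: "The last date of administration of this drug + 28 days".

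Section 10.2 defines incidence as patients with at least one event over "the number of patients included in safety analysis as denominator". It allows exceptions: "If different calculation method from above method is used, it should be described in each table".

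Table 2.9 (section 13.2) states no exception. Its objective is: "Incidence of adverse reactions should be shown by patient characteristics and factor analysis should be conducted". It calls for Fisher's exact test for nominal factors and the Mann-Whitney test for ordinal ones. It specifies no stratification, common cut-off or time-to-event method. Factors found significant are carried into the next table, which splits reactions by seriousness.

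**The concern.** A crude proportion rises with the time a patient is watched. Here the longest window is almost three times the shortest, and calendar start date decides which one a patient gets. Any characteristic whose prevalence differed between early and late starters is then associated with the chance of a recorded reaction, even if it has no effect on the reaction rate.

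Factors that may contribute to safety are one of the three survey objectives in section 4.1, and section 3.1 says the results support the reassessment application. A spurious factor could be reported as a safety signal, or a real one hidden.

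**Working it through.** **The plan's own figures.** 392/7 = 56, 756/7 = 108 and 1120/7 = 160 weeks, so the stated windows are consistent. The ratio of longest to shortest is 1120/392 = 2.86.

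**Incidence by class with the same risk in everyone.** Assume 0.3 reactions per year, with t = weeks/52.

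- Constant hazard, 1 − exp(−0.3t): 27.6%, 46.4% and 60.3% at 56, 108 and 160 weeks.
- Front-loaded hazard with the same 52-week value (Weibull shape 0.5), 1 − exp(−0.3√t): 26.8%, 35.1% and 40.9%.

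**Effect on a harmless factor.** Assume class shares 40/35/25% and factor prevalence 20/30/50% in the 52/104/156-week classes. Among all patients, those with the factor make up 0.080 + 0.105 + 0.125 = 0.310, and those without it 0.320 + 0.245 + 0.125 = 0.690.

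- Constant hazard, factor present: (0.080×0.276 + 0.105×0.464 + 0.125×0.603)/0.310 = 47.2%.
- Constant hazard, factor absent: (0.320×0.276 + 0.245×0.464 + 0.125×0.603)/0.690 = 40.2%. The apparent risk ratio is 47.2/40.2 = 1.17.
- Front-loaded hazard, by the same sums: 35.3% against 32.3%, a ratio of 1.09.

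Reversing the prevalence pattern reverses the direction. Equal prevalence in the three classes removes the difference.

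**False-positive rate of the unstratified Fisher test** (two-sided 5%, simulated under the same rate and prevalence pattern; 20%/year discontinuation is assumed where shown):

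| Setting | n = 200 | n = 400 |
|---|---|---|
| Shares 40/35/25%, constant hazard, full follow-up | about 14% | about 24% |
| Same, with discontinuation | 6–10% | 13–14% |
| Same shares, front-loaded hazard | about 6% | about 8% |
| Same shares, front-loaded hazard and discontinuation | about 5% | about 6% |
| Shares 44/44/11%, constant hazard, full follow-up | about 8% | 12–14% |

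Across repeated runs the front-loaded settings, with or without discontinuation, lie at about 4–9%. A test stratified by follow-up class stays near 5% in every setting, and the crude test is also near nominal when prevalence is equal across classes.

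The 44/44/11% shares come from the SAP's dates under even accrual (assumed). The survey period opens on 16 May 2013 (section 6) and the 156-week class closes on 15 August 2013, which is 92 days against 365 for each other class: 92/822 = 11% and 365/822 = 44%.

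**Factors tied to treatment length by definition.**

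- Days to last administration is capped at 364, 728 or 1092 days after the start date by class (section 10.1).
- Mean daily dose is total dose over number of administrations. On the 160, 80, then 40 mg pattern listed in section 10.1 it equals (40n + 160)/n = 40 + 160/n for n ≥ 2. The section 11 dose bands then only restate n: n = 2 gives 120 mg, n = 4 gives 80 mg, n = 8 gives 60 mg.
- Self-administration needs one check mark at any time, and concomitant steroid counts any overlap with treatment. Longer treatment gives more chance to be classed as present.

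**The case against.** Four points on the other side carry weight.

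- The higher false-positive figures need a constant hazard, full follow-up and a sizeable 156-week class. If reactions come mostly early, or many patients stop, the excess is small. This stands, and it is why a range is given.
- Table 2.7 already reports reactions by onset interval, with denominators matched to observation and Clopper-Pearson intervals. That gives a time-resolved overall picture and weakens any case for changing the overall occurrence tables (2.1, 2.4.1–2.4.3, 2.17). It is not broken down by factor, so it does not repair Table 2.9.
- Table 2.9 is a screen of 28 factors with multiplicity expressly set aside (section 9.5), and a significant result only triggers a descriptive breakdown. No confirmatory error rate is claimed. But setting multiplicity aside accepts chance findings. It does not cover a bias that pushes a given factor in a predictable direction and grows with sample size.
- A reader might infer that named factors, such as prior biologic use or self-administration, are known to have drifted over calendar time, or that every significant factor would be spurious. The SAP supports neither. It gives no prevalence by class, and a factor unrelated to start date or treatment length is compared fairly.

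**Conclusion.** The point holds for Table 2.9. Observation time differs up to 2.86-fold by start date, the outcome is a crude proportion, and the tests ignore the difference. Factors associated with start date or treatment length are biased, in either direction. Others are not.

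The size cannot be fixed from the SAP, which gives no event rate and leaves the number of patients undecided (section 4.3). Under the assumed 0.3 reactions per year and 20/30/50% prevalence, the false-positive rate at n = 200 to 400 ranges from about 4–9% with a front-loaded hazard to 14–24% with constant hazard, full follow-up and shares 40/35/25%. A reader might take the upper end as the expected size, but it is one end of an assumed range. The case for acting rests on the design, and the correction is cheap.

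**What to change.** In Table 2.9, keep the crude rates and do one of the following:

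- Stratify the tests by the follow-up class already defined in section 2: a stratified exact or Mantel-Haenszel test for nominal factors, and the van Elteren test for ordinal ones.
- Count only events within a common 56-week window for all classes, keeping the earlier cut-off for patients who stopped.

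Do not rely on Poisson regression with a patient-time offset. It assumes a constant hazard. Under the front-loaded hazard above its false-positive rate was about 6–11%, no better than the crude test. Reactions per patient-year share this weakness.

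Add a note that days to last administration and mean daily dose are to be read with caution. Both depend on treatment length, and a reaction may itself cause stopping, so stratification alone does not repair them.

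The cost is some programming, since start dates, onset dates and follow-up class are already defined. Stratification loses a little precision. Truncation loses the events after 56 weeks.
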